9.2 Sample Size Determination

A total of 155 participants are planned to be randomized to achieve at least 133 evaluable participants in the Per Protocol analysis set for immunogenicity, assuming a 12% dropout rate for each group. Participants who withdraw from the study will not be replaced.

No confirmatory objectives are planned in this trial; however, the sample size was chosen to allow an exploratory comparison of immunogenicity 28 days after the third administration in Stage 2 (Day 197), between participants receiving full dose of candidate iNTS-TCV vaccine and separate full doses of iNTS-GMMA and TCV vaccines, with respect to Anti-*S. Typhi* Vi Ag total IgG, Anti-*S. Typhimurium* O Ag total IgG, Anti-*S. Enteritidis* O Ag total IgG.

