The IgG against Vi antigen will be determined using GVGH ELISA and the results will be presented in EU/mL unit, which may be further converted to µg/mL, based on correlation with concentration of the standard calibrated against the international standard/another standard already calibrated.

A listing of collection dates and times for the immunogenicity variables will be presented for participants within each treatment group. For each component, the concentration/titer will be listed and summarized by treatment groups across all scheduled timepoints during entire study for each stage. Antibody concentrations/titers for all components will be investigated using Reverse Cumulative Distribution Curves based on the Per-protocol analysis set.

For each study group, each stage, at each timepoint that blood samples are collected for humoral immune response and for each component as measure by ELISA and CCI

- Geometric mean concentrations/titers and their 95% CI will be calculated.
- Within-participant geometric mean ratio (geometric mean at 28 days after each study intervention to each study intervention administration baseline, ie, Day 29 versus Day 1, Day 85 versus Day 57 and Day 197 versus Day 169 and to Day 1 baseline) with their 95% CI will be tabulated.
- Percentage of participants with ≥ 4 fold-increase from Day 1 baseline with their exact 95% CI will be calculated.
- Unadjusted between-group ratio of GMC with 95% CI between iNTS-TCV groups and iNTS-GMMA and TCV groups will be computed for each anti-serotype specific IgG^{1*}, visit, and administration. The unadjusted ratios for each visit will be calculated using results from the corresponding visit as the dependent variable and the treatment group as independent variable. No other covariates will be included in the model.

For each study group, each stage, at each timepoint for S. Typhi Vi component as measured by ELISA:

- The number and percentage of participants with Anti-S. Typhi Vi Ag IgG antibody concentrations \geq CCI and their 95% exact CI will be calculated.
- The number and percentage of participants with Anti-S. Typhi Vi Ag IgG antibody

¹ * Anti- Salmonella Typhi (S. Typhi) Vi antigen (Ag) total IgG, Anti Salmonella Typhimurium (S. Typhimurium) O Ag total IgG, Anti Salmonella Enteritidis (S. Enteritidis) O Ag total IgG will be tested.

concentrations \geq [CC1] and their 95% exact CI will be calculated.

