The above tabulations may be performed by LLOQ status at baseline (above or equal to cut-off versus below the cut-off) for all 3 components, data permitting.

Only for S. Typhi Vi component the above tabulations may be performed by Anti-S. Typhi Vi Ag IgG antibody concentrations status at baseline as measured by ELISA ($>=$ [CC1] and $<=$ [CC1], $>=$ [CC1] and $<=$ [CC1]), data permitting.

Linear mixed model with repeated measures (MMRM) will be used to perform pairwise comparison between full doses of iNTS-TCV and iNTS-GMMA + TCV at Day 29, Day 57, Day 85, Day 169 and Day 197. The model will use fixed effects for center, treatment, time point, treatment*time point, center*treatment, baseline immunogenicity value as covariate, and a repeated time point effect within a participant under an unstructured covariance matrix. Variance between the groups will not be considered equal unless the assumption leads to convergence issues. Additional covariance structures and suitable transformation (e.g., log) may be explored to attain convergence and meet model assumptions, respectively. This analysis will be performed for full doses of iNTS-TCV and iNTS-GMMA + TCV from both the stages.

```
proc mixed data=indsn;  by parameter;  
  class subjid center trta avisit;  
  model aval=center trta avisit trta*avisit center*trta baseline/ddfm=satterth;  
  repeated avisit/subject=subjid type=un group=trta;  
  lsmeans trta*avisitn/pdiff cl alpha=0.05;  
  run;
```

In this analysis, immunogenicity data from full dose group in Europe will be pooled with those from full dose group in Africa if p-value associated to parameter for center*treatment interaction from MMRM model ≥ 0.10 (i.e., suggesting that impact of treatment on immunogenicity endpoint does not depend on center). In that case, GMC, GMRs, and ratio of GMC will be calculated for entire full dose group (i.e., Europe + Africa) adjusted by center from the above MMRM model without the center*treatment interaction term.

In case center*treatment interaction term is significant (i.e., p-value <0.1) the following analyses will be performed: 1) main analysis including center*treatment interaction term and GMC ratio separately for Europe and Africa will be produced from model with center*treatment interaction term, 2) sensitivity analysis excluding center*treatment interaction and GMC ratio for pooled Europe and Africa will be produced from model without center*treatment interaction term.

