The following Table summarizes the statistical analyses:

Document: \\dccar2dnetvnasc01p-lan1.quintiles.net\cp_ops\PROJECTS\Glaxo SmithKline\GSK216152_WZA10802\SAP
Author: PPD Version Number: 2.0
Version Date: 07DEC2023

Template No: CS_TP_BS016 – Revision 7
Effective Date: 01Nov2021

Reference: CS_WI_BS005

Starting Model	P-value for Center*Treatment Interaction	Main Analysis Model	Sensitivity Analysis
center, treatment, center*treatment	≥0.1 drop center*treatment from the model	Starting model without center*treatment term	No sensitivity analysis
time point, treatment*time point, baseline immunogenicity value as covariate	<0.1	Same as the starting model. Output GMC ratio from model with interaction, separately from Europe and Africa	Starting model without center*treatment term

In other words, analysis pooling Europe and Africa data adjusting treatment effect for center variable will be performed in all cases, however in case center*treatment interaction parameter is statistically significant at 0.1 level, it will be considered as sensitivity analysis.

A sensitivity analysis may also be performed pooling Europe and Africa and adjusting treatment effect for race variable if there is evidence of different races at the two centers.

CCI

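### The Stage 2, Day 197 comparison the trial was sized for gets a baseline-adjusted ratio only if the center-by-treatment p-value is below 0.10; a Stage 2-only adjusted model would be a cheap addition

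*SAP*

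**What the plan says.** Protocol 9.2 states that "the sample size was chosen to allow an exploratory comparison of immunogenicity 28 days after the third administration in Stage 2 (Day 197", between full-dose iNTS-TCV and separate full doses of iNTS-GMMA and TCV, for three IgG antigens.

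SAP 15 plans two between-group analyses of these arms.

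- **By-stage ratio.** For each stage and visit, an unadjusted GMC ratio is computed with treatment group as the only term: "No other covariates will be included in the model".
- **MMRM on the full-dose groups of both stages.** "The model will use fixed effects for center, treatment, time point, treatment*time point, center*treatment, baseline immunogenicity value as covariate". If the center-by-treatment p-value is 0.10 or more, that term is dropped and one Europe plus Africa ratio is reported. If it is below 0.10, the main analysis keeps the term and "GMC ratio separately for Europe and Africa will be produced from model with center*treatment interaction term". The SAP's summary table says the same, "Output GMC ratio from model with interaction, separately from Europe and Africa", and the pooled ratio becomes the sensitivity analysis.

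SAP 15 uses baseline in two other places. It plans a "Within-participant geometric mean ratio (geometric mean at 28 days after each study intervention to each study intervention administration baseline", and also against Day 1. It further says "The above tabulations may be performed by LLOQ status at baseline", with a similar option by baseline Vi status. The ANOVA in Protocol 9.4.2 (Table 12) is restricted to participants who have a baseline result, but lists no baseline covariate.

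**The concern.** The Day 1 titre is collected on everyone and is used in the joint model, yet no visible analysis uses it for a Stage 2-only between-group ratio. The within-participant ratios are summaries within a group, and the baseline-status tables are optional. Neither gives an adjusted between-group ratio.

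Whether Stage 2 gets its own adjusted ratio therefore depends on the size of the observed Europe-Africa gap. When it does get one, the model has no center-by-visit or center-by-treatment-by-visit term, so the gap in treatment effect is held equal at all five post-baseline visits.

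The printed code would not produce the separate ratios either. It requests "lsmeans trta*avisitn/pdiff cl alpha=0.05", which has no center, and the visit variable it names appears in neither the CLASS nor the MODEL statement.

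This matters because Protocol 4.2.1 gives the check for interference between components as a purpose of the separate-administration arm, and Protocol 4.2 chose the two locations as low- and high-endemicity settings. With no hypothesis to test, the estimate and its interval are the result.

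**Working it through.** **Evaluable numbers.** Protocol Table 4 gives group sizes 4, 4, 2, 16, 16, 8, 45, 45, 15. Multiplying each by 0.88 (12% dropout, Protocol 9.2) and rounding down gives 3+3+1+14+14+7+39+39+13 = 133, the protocol's figure. The arms of interest have 39 each in Stage 2 and 14 each in Stage 1 Step 2.

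**Assumptions.** The documents give no SD and no correlation. I take a log10 SD of 0.3 to 0.6 and correlations of 0.3, 0.5 and 0.7.

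**Precision of the Stage 2 ratio.** The log10 half-width is t × SD × √(1−ρ²) × √(2/39), where ρ is the correlation of the Day 1 value with the Day 197 value. At SD 0.5 unadjusted: 1.992 × 0.5 × 0.2265 = 0.2255, so the interval is the ratio ×/÷ 10^0.2255 = 1.68. At ρ = 0.5: 1.992 × 0.433 × 0.2265 = 0.195, or ×/÷ 1.57.

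| SD | unadjusted | ρ 0.3 | ρ 0.5 | ρ 0.7 |
|---|---|---|---|---|
| 0.3 | 1.37 | 1.35 | 1.31 | 1.25 |
| 0.4 | 1.51 | 1.49 | 1.43 | 1.35 |
| 0.5 | 1.68 | 1.64 | 1.57 | 1.45 |
| 0.6 | 1.86 | 1.81 | 1.72 | 1.56 |

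The formula 1−√(1−ρ²) gives narrowing of 4.6%, 13.4% and 28.6%. A 6,000-run simulation of ANCOVA against ANOVA, which also pays for estimating the slope, gives about 4%, 13% and 28%. At ρ of 0 to 0.1 the adjusted interval is under 1% wider.

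**What the pooled ratio mixes.** With equal variances, Europe's weight is 14/(14+39) = 26%. If the two stages' ratios differ 2-fold, the pooled ratio lies 2^0.264 = 1.20-fold from the African one.

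**How often a real 2-fold gap is still pooled.** The SE of the interaction is SD × √(v × (2/39 + 2/14)), with 2/39 + 2/14 = 0.194. Here v is the relative variance of the estimate combined over five visits. With equal correlation r between visits, v = (1+4r)/5 without baseline and (1+4r)/5 − r² when baseline is in the model and correlated as the visits are.

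At SD 0.5 and r = 0.5 with baseline: v = 0.60 − 0.25 = 0.35, SE = 0.130, z = 0.301/0.130 = 2.31, and the chance of pooling is Φ(1.645 − 2.31) = 25%. Without baseline: v = 0.60, SE = 0.171, z = 1.76, giving 45%.

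Over equal-correlation and first-order autoregressive structures with r of 0.3, 0.5 and 0.7:

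| SD | baseline correlated as visits are | baseline uninformative |
|---|---|---|
| 0.3 | 0.3–2% | 1–17% |
| 0.4 | 5–13% | 8–38% |
| 0.5 | 16–28% | 22–53% |
| 0.6 | 29–42% | 35–63% |

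The SAP's model contains baseline, so the middle column is the relevant one whenever adjustment would help. The right-hand column applies only where adjustment gains nothing.

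**The case against.** The strongest reply is that the sized comparison is already estimated. The unadjusted Stage 2 ratio is unbiased under randomization, is reported at every visit whatever the interaction p-value, and follows Protocol Table 12. There are no hypotheses (Protocol 9.1), and Protocol 9.6.2 calls the comparisons exploratory and unpowered. All of that stands, and it limits the point to an improvement.

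It also stands that the gain is uncertain. Baseline correlation may be low, because earlier typhoid vaccination is an exclusion (Protocol 5.2.2) and values below the cut-off are set to half the cut-off (SAP 6.1). A pooled ratio is the more precise one if there is truly no gap.

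Three stronger readings are tempting, and the documents do not support them.

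- **That Stage 2 never gets an adjusted ratio.** It does when the interaction p-value is below 0.10.
- **That the pooled ratio replaces the Stage 2 answer.** The by-stage ratio is always shown beside it.
- **That the rule will usually hide a 2-fold gap.** The highest pooling frequencies need an uninformative baseline together with highly correlated visits. An informative baseline also sharpens the SAP's own interaction test, so those frequencies cannot be combined with the largest gain in precision.

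The table shells and the redacted text in SAP 15 are not available, so the statement covers the visible plan only.

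**Conclusion.** The point holds as a low-cost improvement. In the visible plan, the adjusted version of the Stage 2, Day 197 ratio is conditional on the interaction p-value, and even then it comes from a model that holds the Europe-Africa gap constant over visits. The always-reported ratio is valid but may be wider than the collected data allow. The possible gain runs from none to about 28% of the interval width, depending entirely on a baseline correlation that the documents do not give. Where the pooled ratio is the only adjusted one, a 2-fold gap would move it about 1.2-fold from the African value. No bias is shown in the planned Stage 2 ratio, and no claim is made about error rates, power or sample size. No size is put on any distortion of the separate Europe and Africa ratios.

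**What to change.** For each antigen, prespecify a Stage 2-only model on log10 concentration with the log10 Day 1 value as covariate. It can be an ANCOVA at Day 197, or an MMRM with treatment, visit, treatment-by-visit, baseline and baseline-by-visit. Report its Day 197 ratio beside the unadjusted ratio whatever the interaction p-value, and keep the pooled MMRM as supportive.

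If center-specific ratios are still to come from the joint model, add center-by-visit and center-by-treatment-by-visit terms, request LSMEANS by center, treatment and visit, and replace avisitn with avisit.

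The cost is a few lines of SAP and code and one extra table per antigen, with no new data. If baseline proves uninformative, the adjusted interval is under 1% wider. If there is truly no gap, a Stage 2-only ratio has an SE about 17% larger than the pooled one (√(53/39) = 1.17; at SD 0.5, 0.113 against 0.097), which is why the pooled model stays.

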16. SAFETY OUTCOMES

There will be no statistical comparisons between the treatment groups for safety data, unless otherwise specified with the relevant section.

16.1. ADVERSE EVENTS

The analysis of solicited adverse event will be performed in the Solicited Safety Set. The percentage of participants with at least 1 administration site AE (solicited and unsolicited), with at least 1 systemic AE (solicited and unsolicited) and with any AE during the 7-day or the 28-day follow-up period, for each stage, will be tabulated with exact 95% CI after each vaccination and overall. The same calculations will be performed for symptoms rated as grade 3 (severe). This combined analysis of solicited and unsolicited AEs will be performed on the Exposed Set as requested for public disclosure. Solicited

Document: \\dccar2dnetvnasc01p-lan1.quintiles.net\cp_ops\PROJECTS\Glaxo SmithKline\GSK216152_WZA10802\SAP
 Author: PPD Version Number: 2.0
 Version Date: 07DEC2023

Template No: CS_TP_BS016 – Revision 7
 Effective Date: 01Nov2021

Reference: CS_WI_BS005

events and unsolicited AEs will be coded by MedDRA.

The percentage of doses followed by at least 1 administration site AE and by at least 1 systemic AE will be tabulated, overall vaccination course, with exact 95% CI. The same computations will be done for Grade 3 AEs, any unsolicited AEs considered related to vaccination, any Grade 3 unsolicited AEs considered related to vaccination and any AEs resulting in a medically attended visit.

The percentage of participants/doses reporting each individual solicited administration site and systemic AE during the 7-day follow-up period will be tabulated with exact 95% CI as follows:

- Over the 3 doses, the percentage of participants with the symptom and its exact 95% CI.
- Over the 3 doses, the percentage of doses with the symptom and its exact 95% CI.
- At each study dose (visit), the percentage of participants with the symptom and its exact 95% CI.

Occurrence of fever within 7 days post vaccination will be reported per grade, per 0.5°C cumulative increments classes as from $\geq 38^{\circ}\text{C}$ as well as the occurrence of fever $>40^{\circ}\text{C}/104^{\circ}\text{F}$.

Solicited events ongoing after the observation period reported by maximum intensity will be left out of summary tables and only reported in solicited AE listings. Any solicited event with onset day greater than solicited period (i.e., 7 days) will be reported as unsolicited AE and will be included in unsolicited summary tables and listings.

The analysis of unsolicited adverse event will be performed in the Unsolicited Safety Set. The verbatim reports of unsolicited symptoms will be reviewed by a physician and the signs and symptoms will be coded per the Medical Dictionary for Regulatory Activities (MedDRA), Version 26.0 or higher. Every verbatim term will be matched with the appropriate preferred term (PT). The percentage of participants with unsolicited AEs within 28 days after any doses with its exact 95% CI will be tabulated by group, stage and by MedDRA preferred term. Similar tabulation will be done for Grade 3 unsolicited AEs, for unsolicited AEs that resulted in a medically attended visit, for Grade 3 and causally related unsolicited AEs and for unsolicited AEs causally related to vaccination. These tabulations will include System Organ Class (SOC) and SOC/PT analyses.

The number of participants who experienced at least 1 SAE within 28 days after any dose, from dose 1 until 28 days post last dose (Day 197) and from Day 198 until Day 337 will be reported by treatment.

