3.0 OBJECTIVES AND ENDPOINTS

Table 3 Study Objectives and Endpoints

Objectives	Endpoints
Primary	

 • To evaluate the safety and reactogenicity profile of GSK Vaccines Institute for Global Health (GVGH) invasive nontyphoidal Salmonella-typhoid conjugate vaccine (iNTS-TCV) vaccine in healthy European/African adults 	
 • Number of participants in Europe/Stage 1 with solicited administration site and systemic events during 7 days after each study intervention administration (ie, on the day of study intervention administration and the 6 subsequent days) occurring at Day 1, Day 57, and Day 169, by study intervention group • Number of participants in Europe/Stage 1 with unsolicited adverse events (AEs) during 28 days after each study intervention administration (ie, on the day of study intervention administration and the 27 subsequent days) occurring at Day 1, Day 57, and Day 169, by study intervention group • Number of participants in Europe/Stage 1 with serious adverse events (SAEs) from first study intervention administration (Day 1) to 28 days after third study intervention administration (Day 197), by study intervention group • Number of participants in Europe/Stage 1 with AEs/SAEs leading to withdrawal from the study and/or withholding doses of study intervention, from first study intervention administration up to 28 days after third study intervention administration (Day 1 to Day 197), by study intervention group • Number of participants in Europe/Stage 1 with deviations from normal or baseline values for hematological, renal, and hepatic panels test results at 7 days after each study intervention administration (Day 8, Day 64, and Day 176) and at 28 days after each study intervention administration (Day 29, Day 85, and Day 197), by study intervention group • Number of participants in Africa/Stage 2 with solicited administration site and systemic events during 7 days after each study intervention administration (ie, on the day of study intervention administration and the 6 subsequent days) occurring at Day 1, Day 57, and Day 169, by study intervention group • Number of participants in Africa/Stage 2 with unsolicited AEs during 28 days after each study intervention administration (ie, on the day of study intervention administration and the 27 subsequent days) occurring at Day 1, Day 57, and Day 169, by study intervention group • Number of participants in Africa/Stage 2 with SAEs from first study intervention administration (Day 1) to 28 days after third study intervention administration (Day 197), by study intervention group • Number of participants in Africa/Stage 2 with AEs/SAEs leading to withdrawal from the study and/or withholding doses of study intervention, from first study intervention administration up to 28 days after third study intervention administration (Day 1 to Day 197), by study intervention group

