6.1. SUMMARY STATISTICS

For qualitative variables, the population size (N for sample size and n for available data) and the percentage (of available data) for each class of the variable will be presented. Quantitative variables will be summarized using descriptive statistics, including N (with data available), mean, standard deviation (SD), median, Q1, Q3, minimum, and/or maximum values. Geometric mean will be included for immunogenicity parameters together with 95% confidence interval (CI), where applicable.

The exact two-sided 95% CIs for a proportion within a group will be calculated using the Clopper-Pearson exact method. The geometric mean antibody concentrations (GMCs) and titers (GMTs) calculations will be performed by taking the anti-log of the mean of the log10 titer transformations. Confidence interval for geometric means will be derived by raising 10 to the confidence interval associated with mean of log10 values i.e., CI of geometric mean = $10^{(CI \text{ for the mean of log10 values})}$. All participants with valid data will be considered. Participants whose antibody titers are below the cut-off of the assay will be given an arbitrary value of half the cut-off for the purpose of GMC/GMT calculation.

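### SAP 16.1 puts Clopper-Pearson intervals on percentages of doses, as if up to three doses from one participant were independent (minor: descriptive rows only)

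*SAP*

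**What the plan says.** SAP 16.1 lists three rows for each individual solicited event. One of them is the dose-level row, "Over the 3 doses, the percentage of doses with the symptom and its exact 95% CI". The same section adds summary rows: "The percentage of doses followed by at least 1 administration site AE and by at least 1 systemic AE will be tabulated", over the whole vaccination course and with an exact 95% CI. Those are repeated for Grade 3 AEs, related unsolicited AEs, and "any Grade 3 unsolicited AEs considered related to vaccination and any AEs resulting in a medically attended visit".

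The method comes from SAP 6.1: "The exact two-sided 95% CIs for a proportion within a group will be calculated using the Clopper-Pearson exact method". No other method is given for doses.

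Each participant is dosed on Day 1, Day 57 and Day 169 (Protocol 4.1, SAP 3.1). Protocol Table 11 asks for percentages of doses to be tabulated and does not ask for a confidence interval on them.

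**The concern.** Clopper-Pearson limits come from a binomial model with independent trials. Percentages of doses pooled over the course do not fit that model, because the denominator can hold three doses from the same person. Someone who reports pain or fatigue after one dose may be more likely to report it after the next. With positive correlation, 135 doses from 45 people carry less information than 135 doses from 135 people.

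At stake is the honesty of a label. A reader takes an exact 95% CI to cover at least 95% of the time. In a first-in-human safety table, the usual harm would be an upper limit that reassures more than the data allow.

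**Working it through.** The documents state no figure for a dose-level interval, so there is nothing to reproduce first.

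**Inputs from the documents**
- Doses per participant: up to 3 (Protocol 4.1).
- Group sizes (Protocol Table 4): Stage 2, 45 / 45 / 15; Stage 1 Step 2, 16 / 16 / 8; Stage 1 Step 1, 4 / 4 / 2. SAP 6.2 shows a single Stage 1 Placebo column, so 2 + 8 = 10.
- Denominators: 45 x 3 = 135 doses; 16 x 3 = 48; 15 x 3 = 45; 10 x 3 = 30; 4 x 3 = 12.
- Interval: two-sided 95% Clopper-Pearson on total doses (SAP 6.1).

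**Assumptions**
- Neither document gives an ICC or event rates. ICC is taken as 0, 0.1, 0.3 and 0.5, and the true per-dose rate as 5% to 50%.
- One ICC is assumed for all pairs of doses. This is least plausible in Control_Stage 2, where the three doses are three different vaccines.

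**Coverage**

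The number of doses with the event in one participant follows a beta-binomial on 3 doses. Summing over participants by convolution gives the exact distribution of the group total. Coverage is the probability that the Clopper-Pearson interval on that total contains the true rate. Means over 200 equally spaced rates from 5% to 50%:

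| Participants | ICC 0 | ICC 0.1 | ICC 0.3 | ICC 0.5 | Mean first below 95% at ICC about |
|---|---|---|---|---|---|
| 45 | 96.1% | 94.1% | 89.7% | 85.5% | 0.06 |
| 16 | 96.7% | 94.9% | 90.9% | 86.8% | 0.10 |
| 15 (Control) | 96.8% | 95.0% | 91.0% | 86.9% | 0.10 |
| 10 (Stage 1 Placebo) | 97.2% | 95.5% | 91.8% | 87.9% | 0.13 |
| 4 | 98.1% | 96.8% | 93.8% | 90.6% | 0.23 |

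The last column was searched in ICC steps of 0.01.

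**Rare events.** The means leave out rates below 5%, where the loss is smaller. With 45 participants, coverage at true rates of 1% and 2% is 96.2% and 94.9% at ICC 0.3, and 94.7% and 93.2% at ICC 0.5. With 16 participants at a 5% rate and ICC 0.3 it is 96.7%.

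**Width**

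For three doses the design effect is D = 1 + (3 - 1) x ICC = 1 + 2 x ICC. Applying Clopper-Pearson to x/D events in N/D doses, with 27/135 (20%) as the example:
- As written, D = 1: 13.6% to 27.7%.
- ICC 0.1, D = 1.2, 22.5/112.5: 13.1% to 28.6%.
- ICC 0.3, D = 1.6, 16.9/84.4: 12.1% to 30.1%.

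With 0/135 the upper limit as written is 2.7%. It becomes 4.3% at ICC 0.3, and 7.9% in the extreme case of ICC 1, which is the same as 0/45.

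**The case against.** The strongest reply is that nothing depends on these intervals. SAP 16 says "There will be no statistical comparisons between the treatment groups for safety data, unless otherwise specified with the relevant section". The primary endpoints count people, for example "Number of participants in Europe/Stage 1 with solicited administration site and systemic events during 7 days after each study intervention administration", and so do the holding rules in Protocol Table 5. Protocol 9.1 sets no formal hypotheses. For each solicited symptom, a valid interval for the risk after one dose stands beside the criticised row: "At each study dose (visit), the percentage of participants with the symptom and its exact 95% CI". All of this stands, and it is why the point is minor. The iSRC and SRT analyses are described in a separate document and could not be checked.

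A second reply is that Clopper-Pearson is conservative and absorbs mild correlation. It does, up to the thresholds in the table. Below them there is no practical problem, and rare events can stay close to nominal at higher ICCs. The loss concerns mainly common reactions, at moderate ICC and in the larger groups. Its size rests on an assumed ICC.

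A third reply is that the table shells may already carry a footnote. The shells are not in the documents reviewed, so this is possible. The SAP text itself has no such caveat.

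Finally, the participant-level tables may not mirror every dose-level row. For medically attended events they do not: the participant-level plan is "Similar tabulation will be done for Grade 3 unsolicited AEs, for unsolicited AEs that resulted in a medically attended visit", which covers unsolicited AEs only, while the dose-level row covers any AE. If the dose-level rows for related AEs also keep the administration site and systemic split, they too lack an exact counterpart, because no such split is stated for the participant-level tables of related unsolicited AEs. This affects how many rows to add if intervals are wanted there. It does not affect the case for removing or qualifying the dose-level intervals.

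**Conclusion.** The concern holds, as a minor point. The dose-level intervals rest on an independence assumption that repeated dosing does not support. Averaged over true rates of 5% to 50%, coverage in groups of 15 to 45 is about 90% to 91% at ICC 0.3 and 86% to 87% at ICC 0.5. At ICC 0.1 it is 94.1% to 95.0%. These figures assume one common ICC, three doses from every participant, and a beta-binomial model. Point estimates and all participant-level intervals, overall and at each dose, are unaffected.

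**What to change.** In SAP 16.1, drop the confidence interval from all percent-of-doses rows and keep the point estimates. Nothing the protocol asks for in those rows is lost. The participant-level exact intervals already planned then carry the uncertainty. If an interval is wanted for all medically attended AEs, add a participant-level row, and check whether the related-AE rows need the same. The cost is a wording and table-shell change plus any added row.

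If per-dose intervals are kept, make them participant-clustered. One option is Clopper-Pearson on doses divided by an estimated design effect held between 1 and 3, with the effective sample size set to the number of participants when there are no events or the group is too small, such as the groups of 4. The SAP must state how the design effect is estimated. In 40,000 simulated datasets per setting (rates 2% to 50%, ICC 0 to 0.7; 45, 16, 15 and 10 participants), coverage was 94.7% to 99.4%, against 79.7% to 99.3% for the interval as written. The price is a short extra program and wider intervals: for rates of 20% and 50% in groups of 16 and 45, median width is about 1.28 times at ICC 0.3 and 1.45 times at ICC 0.5. In groups of 4 the fallback is conservative (99.5% to 100%).

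At the least, footnote these rows to say that the interval does not account for repeated doses in the same participant.
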